2.6. Sample Size Determination

The co-primary endpoints will be analyzed using an overall Type I error rate of 0.01 for PFS and 0.04 for OS. To detect a hazard ratio (experimental vs. control) of 0.70 with approximately 85% power, 419 PFS events (PD/Deaths) are required to be observed; this assumes a median (ITT) PFS of 8.0 months (34.7 weeks) for the experimental arm (neratinib plus capecitabine) and 5.6 months (24.3 weeks) for the control arm (lapatinib plus capecitabine).

It is expected that the 419th event will be observed at approximately 26 months after the first subject is enrolled, which would correspond to approximately half of the death events needed to be observed. At this time, an interim analysis on OS will also be performed. For the OS endpoint, a group sequential method will be employed to maintain the overall Type I error rate at 0.04. Specifically, Lan DeMets alpha spending function approximating the O’Brian-Fleming boundaries will be calculated to create appropriate critical values to which the log rank statistic will be compared (De Mets and Gordon Lan, 1994). If 50% of the deaths are observed at the interim OS analysis, the boundary using the Lan-DeMets alpha spending function is shown in Table 1 for OS interim analysis.

Table 1: Spending Function

Information Fraction	Expected Death Events	Study Month	Boundary (Reject H_0)	2-Sided Significance Level*
50%	185	26	3.066	0.002
100%	378	50	2.058	0.039

* This significance level relates to the 0.04 alpha allocation to OS but will be updated if the entire 0.05 can be allocated to OS.

These boundaries are designed to detect a hazard ratio (experimental vs. control) of 0.725 with approximately 85% power. Overall, 378 OS events (deaths) are required to be observed; this assumes a median (intent to treat [ITT]) OS of 30.3 months for the experimental arm (neratinib plus capecitabine) and 22.0 months for the control arm (lapatinib plus capecitabine).

Approximately 600 subjects will be enrolled and randomized equally between the two treatment arms. This sample size assumes a 1% drop out rate per 12 months (52 weeks) equally distributed between the treatment arms for the PFS endpoint.

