8.3.2. Secondary Efficacy Analyses

The secondary endpoints of ORR, CBR and duration of response will be assessed using the centrally reviewed tumor assessments as well as the investigator tumor assessments. The secondary endpoint of time to intervention for symptomatic CNS disease will only use the investigator-reported data.

The treatment difference in the secondary efficacy endpoint of investigator assessed PFS will be assessed with the product limit estimate of the median time to event. Differences between treatment groups will be examined using a log rank test statistic stratified by hormone receptor status, number of prior HER2-directed regimen in the metastatic setting, visceral disease status, and geographic region strata (similar to the analyses for the primary endpoints). All time-to-event endpoints including time to intervention for symptomatic CNS disease will be displayed using a Kaplan-Meier survival plot.

For the secondary endpoints of ORR and CBR the subjects included in the analyses are those that had measurable disease (per RECIST v1.1) at screening. Any tumor assessments after the start of new anti-cancer therapy will not be included in the analyses for these two endpoints. The treatment difference in the secondary efficacy endpoints of ORR and CBR will be analyzed using a Cochran-Mantel-Haenzel (CMH) Chi-square test, stratified on hormone receptor status, number of prior HER2-directed regimens in the metastatic setting, geographic region and disease category (visceral vs. non-visceral only).

Duration of response will be summarized by treatment group for the patients that responded. If there are patients that continue to respond, they will be censored at their last tumor assessment and a Kaplan-Meier analysis will be done to estimate the duration of response.

With the exception of the CNS endpoint, which will be tested only after the null hypothesis is rejected for OS; all other secondary endpoints are descriptive analyses and will be done at the time of the primary PFS analysis.

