2.5.6. Completion rate

A completion analysis will be done to evaluate the magnitude of missing assessments. The completion analysis will focus on the following scales.

1. QLQ-C30 – the C30 summary subscale (required non-missing subscale scores from all except financial difficulty, the most conservative scale from C30)
2. BR-23 - the systemic therapy sides effects subscale
3. EQ5D-5L - either the VAS or Index Score

Completion is defined as:

- Overall: The actual number of assessments (baseline and all post baseline assessments) / expected number of assessments (from baseline to last assessment thru last dose date+28 days)*100%.
- Calculation for expected number of assessments will be based on treatment duration and corresponding cycle of last dose day. If last dose day falls in a day in cycle Y which is the completion of an even cycle , the expected number of HOA assessments will be the integer part of $(Y/2) + 1$; or else If last dose day falls in a cycle Y and $Y/2$ does not yield a whole number then , the expected number of HOA assessments will be the integer portion of $(Y/2) + 2$.

For example, a subject with the last dose in cycle 4 would be expected to have 3 assessments (Baseline, cycle 3 and EOT). If there are multiple assessments on the same day only one assessment will be counted for that day. Lastly, if the completion is greater than 100%, it will be truncated at 100%.

- Completion at each scheduled visit: The number of subjects that completed the scale flagged for the scheduled visit divided by the number of subjects under treatment in the corresponding cycle.

The overall completion rate and completion rate by visit will be summarized by treatment group for each relevant scale.

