2.5.7. Pattern Mixture Model Analysis

After reviewing findings from the descriptive statistics, the overall completion rate, and the scheduled visit specific completion rate analysis if there exists a pattern of missing assessments additional sensitivity analysis like pattern mixture model analysis may be added in an ad hoc fashion.

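### The overall quality-of-life completion formula expects an end-of-treatment form even from subjects still on treatment at the cutoff, so full compliance can score a few points below 100%

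*SAP*

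**What the plan says.** Supplemental SAP 2.5.6 sets up a completion analysis to show how much questionnaire data is missing. The overall rate is the actual number of assessments over the expected number, capped at 100%. With Y the cycle of the last dose, the expected number is int(Y/2) + 1 for even Y and int(Y/2) + 2 for odd Y. The section illustrates this: "For example, a subject with the last dose in cycle 4 would be expected to have 3 assessments (Baseline, cycle 3 and EOT". It also gives a by-visit rate, whose denominator is the subjects under treatment in the corresponding cycle.

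The protocol synopsis (Health Outcomes Assessment) schedules the forms at screening, 6-weekly on treatment, and at treatment discontinuation. Protocol Appendix 1, footnote i, places the 6-weekly form at the end of every second cycle, within 3 days either way. Supplemental SAP 2.4.1 maps these forms to Day 1 of Cycles 3, 5, 7 and so on.

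On timing, SAP 8.3.2 says that, the CNS endpoint apart, "all other secondary endpoints are descriptive analyses and will be done at the time of the primary PFS analysis". SAP 8.3.1 triggers that analysis at 419 centrally assessed PFS events.

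Supplemental SAP 2.5.7 makes a pattern mixture analysis optional, to be considered "After reviewing findings from the descriptive statistics, the overall completion rate, and the scheduled visit specific completion rate analysis".

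**The concern.** A discontinuation form exists only once treatment has stopped. The 419-event analysis takes place while some patients are still on study drug. Supplemental SAP 6.2 recognises this for time to treatment failure, where such patients are censored at the cutoff, but 2.5.6 has no matching branch.

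Run as written, with the latest dose before cutoff standing in for the last dose day, the formula counts a form that could not yet exist. The overall rate then mixes administrative cutoff with genuine non-completion. It is reported by arm, and more patients should be ongoing in the arm with the longer planned PFS, so part of any arm difference could be an artefact.

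**Working it through.** **Inputs from SAP 2.6.** "0.70 with approximately 85% power, 419 PFS events (PD/Deaths) are required to be observed"; PFS alpha 0.01 (two-sided assumed); planned median PFS "8.0 months (34.7 weeks) for the experimental arm (neratinib plus capecitabine) and 5.6 months (24.3 weeks) for the control arm"; about 600 patients, allocated 1:1; dropout of 1% a year in each arm; 419th event expected at about month 26.

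**Reproducing the plan's figures.** Freedman's formula gives (2.576 + 1.036)² × (1.70/0.30)² = 419 events, as stated. The worked example also reproduces: last dose in cycle 4 gives 4/2 + 1 = 3.

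**The count, cycle by cycle.** By cycle Y the on-treatment schedule has produced baseline plus one form at each odd cycle from Cycle 3, that is 1 + int((Y-1)/2). The even branch is read as covering any last dose in an even cycle, as the worked example implies.

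| Cycle Y | Expected by 2.5.6 | On-treatment forms | Score of a compliant ongoing subject |
|---|---|---|---|
| 1-2 | 2 | 1 | 50% |
| 3-4 | 3 | 2 | 67% |
| 5-6 | 4 | 3 | 75% |
| 7-8 | 5 | 4 | 80% |
| 9-10 | 6 | 5 | 83% |

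The exception is the 3-day window. A subject who completes the next 6-weekly form up to 3 days early, at the end of an even cycle, already holds the full number. If every form were completed 3 days early, that would be about 3/42 = 7% of ongoing subjects.

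**How many could be affected.** Without a PFS event at the trigger: (600 - 419)/600 = 181/600 = 30.2%. The share on treatment can only be lower.

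**Size under the design assumptions.** Accrual is not stated. Uniform accrual over R = 23.85 months puts 419 events at month 26. With exponential PFS and 1% yearly dropout, the total hazard h is 0.0875 per month on neratinib and 0.1246 on lapatinib. The share ongoing is [exp(-h(26 - R)) - exp(-26h)]/(hR):

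- neratinib: (0.8285 - 0.1029)/2.086 = 34.8%
- lapatinib: (0.7650 - 0.0392)/2.972 = 24.4%

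In simulation (1,000,000 patients per arm, perfect compliance, every progression-free patient on treatment), ongoing patients average 85.3% and 83.9%. The arm means are therefore:

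- neratinib: 100 - 34.8% × 14.7 = 94.9%
- lapatinib: 100 - 24.4% × 16.1 = about 96.0%

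Rounding accrual to 24 months gives 94.7% v 95.9%.

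**Sensitivity (neratinib v lapatinib, perfect compliance).**

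| Assumption | Overall completion |
|---|---|
| 75% of progression-free patients on treatment | 96.2% v 97.1% |
| 50% | 97.4% v 98.0% |
| 33% | 98.3% v 98.7% |
| Extra stopping 2-4% per month, both arms | 95.4-96.0% v 96.4-96.8% |
| Extra stopping 4% per month neratinib, 1% lapatinib | 96.0% v 96.1% |
| Extra stopping 4% per month neratinib, none lapatinib | 96.0% v 95.9% |
| Accrual 20 months (460 events by month 26) | 97.2% v 98.1% |
| Accrual 26 months (390 events by month 26) | 92.0% v 93.2% |

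The two accrual rows do not match the planned 419 events at month 26; they only bound the effect.

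**The case against.** **The rule is silent rather than wrong.** It is keyed to the last dose day, which is not defined for someone still dosing. That is fair: the shortfall appears only if the latest dose before cutoff is used. On any other reading the rate is undefined for these subjects, so a rule is needed either way.

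**Progression-free is not the same as on treatment.** A reader might infer that 30% of patients are mis-scored. The documents do not support that. The 181 include patients who stopped for toxicity, patients who stopped on investigator-called progression without a central event, and patients censored for new therapy or missed assessments (SAP 8.2.1). All of these are off drug and can have a discontinuation form. The objection stands, and 30% is a ceiling. It may not be a remote one: the planned average of 9.5 months on treatment (Protocol 4.1) is close to the mean PFS implied by the two medians, (8.0 + 5.6)/2 ÷ 0.693 = 9.8 months.

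**The arm direction is not assured.** A reader might infer that the formula necessarily disadvantages neratinib. It does so only under the planned hazard ratio and similar non-progression stopping in both arms. The gap vanishes if about 30% of neratinib stops, and no lapatinib stops, are for reasons other than progression.

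**Little depends on the number.** A reader might infer that the artefact would decide whether a pattern mixture analysis is run. Supplemental SAP 2.5.7 sets no threshold and looks at three inputs together, and SAP 8.3.3.2 already names pattern mixture models among the sensitivity analyses. By-visit completion does not count the EOT form in this way and would help expose the artefact. The protocol synopsis also plans an analysis of all efficacy endpoints after long-term follow-up, when few patients should be on treatment. All of this stands. It limits the importance of the point but does not make the count correct.

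**Conclusion.** The point holds as a minor one. The expected count in 2.5.6 includes a discontinuation form for everyone and has no branch for subjects on treatment at the cutoff. With the latest dose before cutoff as the last dose day, a compliant ongoing subject is generally one form short, apart from those who completed the next form early at the end of an even cycle.

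Under the planned medians and an assumed uniform accrual of about 24 months, perfect compliance scores about 95% v 96%, or about 96-98% if half to three quarters of progression-free patients are still on treatment. The gap of about one point between arms depends on similar non-progression stopping. No treatment comparison of quality-of-life scores uses this rate, so the documents give no ground for inferring bias in those comparisons from it.

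**What to change.** In Supplemental SAP 2.5.6, add that for a subject on study treatment at the data cutoff:

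- no EOT form is expected;
- Y is the cycle of the latest dose on or before the cutoff;
- the expected number is baseline plus the 6-weekly forms due by the cutoff, that is 1 + int((Y-1)/2), with a form at the end of an even cycle counted once its 3-day window has closed.

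Keep the present formula for subjects who have discontinued. The existing cap at 100% already handles a form completed early. With this rule, perfect compliance scores 100% in both arms, and an ongoing subject who misses a due form is still counted as missing it.

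The cost is a sentence or two in the Supplement and one condition in the program. No new data are needed.

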2.5.7. Pattern Mixture Model Analysis

After reviewing findings from the descriptive statistics, the overall completion rate, and the scheduled visit specific completion rate analysis if there exists a pattern of missing assessments additional sensitivity analysis like pattern mixture model analysis may be added in an ad hoc fashion.

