8. EFFICACY EVALUATION

8.1. Overview of Efficacy Analysis Issues

8.1.1. Handling of Dropouts or Missing Data

Missing assessments for PFS, the number of subjects who drop out prior to PFS or OS, and the length of follow up for dropouts will be summarized by treatment group. Sensitivity analyses will be performed to assess the impact of subject dropout or missing assessments on the primary efficacy analyses.

Other endpoints that could be affected by missing values (e.g. health outcome assessments) will be analyzed using a sensitivity analysis to quantify the impact of missing values in the results.

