8.3.3.2. Analysis of Health Outcome Assessments

Patient-reported health-related quality of life measures (EORTC QLQ-C30 and EQ-5D) will be summarized by treatment group and visit. Differences between treatment groups will be described using an F test from a random effects mixed model with treatment, time, number of prior HER2-directed regimens in the metastatic setting (binary), geographic region, hormone receptor status, disease category, and the treatment by time interaction.

Endpoints that could be affected by missing values (e.g., health outcomes assessments) will be analyzed using a sensitivity analysis, including pattern mixture models. Results will be summarized by treatment group and visit.

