2. ANALYSIS OF QUALITY OF LIFE DATA

This section expands on the QoL analysis described in sections 8.3.3.1-8.3.3.2 of the Statistical Analysis Plan (SAP) version 2.1.

In summary, there were three Quality of Life (QoL) instruments used in the NALA study: QLQ-C30, BR-23, and EQ-5D-5L. There are 26 scales in these instruments and they are presented in [Table 1](#) (QLQ-C30: 16 scales, BR-23: 8 scales, VAS and EQ-5D-5L health index score). The HOA instruments are administered every 2 cycles (6 weeks) until the end of study drug administration.

Table 1: Quality of Life Instruments and Scales

	Scale	Number of items	Score Range	Version 3.0 Item Numbers	Function or Symptom Scales	
QLQ-C30 Summary Score	C30Sum	13	0-100	1-28, 30	F	QLQ-C30
Global Health status/QoL						
Global health status/QoL	QL2	2	0-100	29, 30	F	QLQ-C30
Functional Scales						
Physical functioning	PF2	5	0-100	1 to 5	F	QLQ-C30
Role Functioning	RF2	2	0-100	6,7	F	QLQ-C30
Emotional Functioning	EF	4	0-100	21 to 24	F	QLQ-C30
Cognitive Functioning	CF	2	0-100	20, 25	F	QLQ-C30
Social Functioning	SF	2	0-100	26, 27	F	QLQ-C30
Symptom Scales						
Fatigue	FA	3	0-100	10, 12, 18	S	QLQ-C30
Nausea and vomiting	NV	2	0-100	14, 15	S	QLQ-C30
Pain	PA	2	0-100	9, 19	S	QLQ-C30
Dyspnoea	DY	1	0-100	8	S	QLQ-C30
Insomnia	SL	1	0-100	11	S	QLQ-C30
Appetite loss	AP	1	0-100	13	S	QLQ-C30
Constipation	CO	1	0-100	16	S	QLQ-C30
Diarrhea	DI	1	0-100	17	S	QLQ-C30
Financial difficulties	FI	1	0-100	28	S	QLQ-C30

Table 1: Quality of Life Instruments and Scales (continued)

	Scale	Number of items	Score Range	Version 3.0 Item Numbers	Function or Symptom Scales	
Functional Scales			0-100			
Body Image	BRBI	4	0-100	9-12	F	BR23
Sexual Functioning	BRSEF	2	0-100	14, 15	S	BR23
Sexual Enjoyment	BRSEE	1	0-100	16	S	BR23
Future Perspective	BRFU	1	0-100	13	F	BR23
Symptom Scales/Items			0-100			
Systemic therapy side effects	BRST	7	0-100	1-4, 6, 7, 8	S	BR23
Breast Symptoms	BRBS	4	0-100	20-23	S	BR23
Arm Symptoms	BRAS	3	0-100	17, 18, 19	S	BR23
Upset by hair loss	BRHL	1	0-100	5	S	BR23
EQ-5D-5L Health State Summary Score	VAS		-0.595 – 1.000		F	EQ-5D-5L
EQ-5D-5L Index Score	IndexS		0-100		F	EQ-5D-5L

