2.1.1. QoL populations

In the 1301 SAP version 2.1 the QoL population was defined as a single population across all the HOA instruments. After the approval of the SAP it was determined that it would be best to define a separate population for each of the subscales. A subject will be included in the population for a particular subscale if they are in the safety population and they had a baseline assessment for that subscale as well as at least one post baseline assessment (up to last dose day +28 days) for the specific subscale. In the analysis dataset there will be a flag for each subscale population.

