2.5.4. Time To Deterioration (TTD) Analysis

For TTD analysis, all records (including multiple assessments within a visit window post baseline assessment) sorted in chronological order will be used to identify the first event. This analysis will be done for the 7 subscales listed in Section 2.5.3

Time to deterioration is defined as the time from Baseline to:

1. Function scales: to the first assessment date where a 10 point or more decrease was observed for the scale of interest
2. Symptom scales: to the first assessment date where a 10 point or more increase was observed for the scale of interest.

If subject's score change did not reach the deterioration threshold value they will be censored at their last HOA assessment. If a subject dies (occurred on or before last dose date plus 28 days) prior to a documented decline in HOA assessment, the subject will be considered to have the deterioration event on the death date unless the date of death occurs after 2 missed HOA assessments (12 weeks + 3 days), in that case, the subject will be censored at last QOL assessment prior to death.

The log-rank test from a Kaplan-Meier method will be used to assess treatment differences. In addition a Cox Proportional Hazards model including treatment arm, prior HER2-directed regimens in the metastatic setting (2 or 3+), hormone receptor status (positive or negative), and disease location (visceral and non-visceral) will be used to estimate the hazard ratio. The use of three of the four randomization strata is documented in a Note to file dated 6-SEP-2018.

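### The Supplement makes the SAP's quality-of-life missing-data analysis optional after results are seen, and its population rule removes some deaths that its time-to-deterioration rule counts as events

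*SAP*

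**What the plan says.** **Missing data.** Protocol section 12.3.2.1 and SAP section 8.1.1 both promise a sensitivity analysis for endpoints exposed to missing values and give health outcomes as the example. The SAP wording is that they "will be analyzed using a sensitivity analysis to quantify the impact of missing values in the results". SAP section 8.3.3.2 names a method: these endpoints "will be analyzed using a sensitivity analysis, including pattern mixture models".

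Supplement section 2.5.7 sets a condition. The decision comes "After reviewing findings from the descriptive statistics, the overall completion rate, and the scheduled visit specific completion rate analysis if there exists a pattern" in which forms are absent, and then "additional sensitivity analysis like pattern mixture model analysis may be added in an ad hoc fashion". Section 2.5.6 defines the completion rates that feed that review and reports them by arm: "The overall completion rate and completion rate by visit will be summarized by treatment group for each relevant scale". On the schedule, Supplement section 2 says: "The HOA instruments are administered every 2 cycles (6 weeks) until the end of study drug administration".

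**Deaths.** Supplement section 2.5.4 provides that if a patient dies within 28 days of the last dose with no earlier documented decline, "the subject will be considered to have the deterioration event on the death date". The exception is a death that follows two missed assessments (12 weeks plus 3 days), which is censored. Supplement section 2.1.1 limits each subscale population to safety-population patients with a baseline score "as well as at least one post baseline assessment" of that subscale. SAP section 4.4 already had the same requirement across instruments, and SAP section 4 assigns quality-of-life analyses to that population.

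**The concern.** The main quality-of-life model is a repeated-measures mixed model on observed scores, which is valid if scores are missing at random. Patients stop completing forms when they stop drug, and they stop drug because of progression, toxicity or death, so that assumption needs a check. A check that may or may not be run, on a trigger with no criterion, after by-arm results have been read, does not work as a prespecified check.

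The second issue is selection. Counting death as deterioration is meant to stop the worst outcomes from disappearing. Requiring a post-baseline score removes exactly the patients who die too early to give one. Whichever arm has more such deaths will look better than it should.

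What is at stake is the credibility of the comparison on a named secondary objective in an open-label trial, not a confirmatory claim.

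**Working it through.** The documents give no figure for this point, so there is none to reproduce. Steps 1 to 3 compare texts, and step 4 is an illustration of size.

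**1. Status of the sensitivity analysis**

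| Source | Status | Method named | Condition |
|---|---|---|---|
| Protocol 12.3.2.1 | firm | none | none |
| SAP 8.1.1 | firm | none | none |
| SAP 8.3.3.2 | firm | pattern mixture models | none |
| Supplement 2.5.7 | optional, ad hoc | pattern mixture as an example | after review of results, if a pattern exists |

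Supplement 2.5.7 does not define a pattern or set a threshold, and the Supplement's Table 2 of planned tables has no pattern-mixture entry. The mixed model (2.5.2), the response analysis (2.5.3) and the AUC (2.5.5) all use observed scores. If 2.5.7 is not invoked, the Supplement contains no missing-data sensitivity analysis for quality of life.

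**2. What the completion rates can show.** In section 2.5.6 the overall denominator is the number of forms expected from treatment duration, and the by-visit denominator is the number of patients under treatment in that cycle. The Supplement's own example is a patient whose last dose falls in cycle 4: expected forms = 4/2 + 1 = 3 (baseline, cycle 3, end of treatment). If all three are returned, completion is 3/3 = 100%, although the patient contributes no score at any later cycle. Both arms can therefore show high completion while differing widely in how many patients still have scores. The by-visit patient counts in the descriptive tables would fall, but nothing says how large a fall or imbalance should trigger the analysis.

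**3. The two rules on deaths.** Take a patient with a baseline score who starts drug, returns no post-baseline form, and dies before two assessments have been missed and within 28 days of the last dose.

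- Under Supplement 2.5.4 this patient is an event on the date of death.
- Under Supplement 2.1.1, applied through SAP section 4, this patient is not in the population.

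Section 2.5.4 names no population of its own that would settle the matter. The conflict is limited to patients with no post-baseline form at all. Protocol section 9.3 and Appendix 1 schedule a questionnaire at the treatment discontinuation visit, 0 to 3 days after the last dose, and the first post-baseline window in Supplement 2.4.1 opens on Day 2. A patient who completes that form and then dies stays in and is counted.

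**4. Ceiling on the number affected**

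Inputs:
- OS medians of 22.0 months (control) and 30.3 months (neratinib), from SAP 2.6. Their ratio, 22.0/30.3 = 0.726, agrees with the stated hazard ratio of 0.725.
- 600 patients randomized 1:1, so 300 per arm (SAP 2.6).
- First scheduled post-baseline form at Day 43 (Supplement 2.4.1).
- Limit of the death rule for a patient with no form: 12 × 7 + 3 = 87 days (Supplement 2.5.4).
- Assumptions: exponential survival, time counted from randomization, 30.4375 days per month.

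Formula: deaths by day t = 300 × (1 − exp(−ln 2 × (t/30.4375)/median)).

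| Day | Control | Neratinib | Total |
|---|---|---|---|
| 43 | 300 × 0.0435 = 13.1 | 300 × 0.0318 = 9.5 | 22.6 (3.8% of 600) |
| 87 | 300 × 0.0861 = 25.8 | 300 × 0.0633 = 19.0 | 44.8 (7.5% of 600) |

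The Day 43 row is the ceiling for deaths before the first scheduled form. The Day 87 row is a looser ceiling that also admits patients who missed the Day 43 form. Both rows include patients who are not in conflict: those with a discontinuation form or another post-baseline form, those who died more than 28 days after the last dose, those with no baseline score, and those never dosed.

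**The case against.** The Supplement never withdraws the SAP commitment. Sections 1 and 2 present it as further description of the SAP, and where it departs from the SAP on the quality-of-life population (2.1.1) it says so. Section 2.5.7 carries no such statement. A reader might infer that the analysis has been cancelled. The documents do not support that: they show two texts that disagree. The SAP commitment was also thin, naming pattern mixture models without patterns, identifying restrictions or a planned table. This stands, and it is why the fix must specify the model as well as restore the commitment.

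A reader might also infer that a missing-data pattern is certain by design, and turn the planned PFS curves into missingness rates. That fails too. No questionnaire is scheduled after the discontinuation visit, so under the Supplement's definitions later scores are unscheduled, not missing, and whether to model them is a choice of estimand. What remains is that completion rates defined this way cannot show the loss.

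On deaths, it is tempting to say that most patients who die before Day 43 would be excluded. The discontinuation form, and the instruction in protocol section 10.3 to make every effort to complete that visit, leave no basis for saying most. The requirement for a post-baseline score also began in SAP 4.4. The Supplement's part was to apply it per subscale and to add a death rule that does not fit it.

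Finally, SAP sections 8.3 and 8.3.2 make every secondary endpoint except CNS intervention descriptive. That stands, and it limits the consequence.

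**Conclusion.** Both parts hold in this limited form.

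First, SAP 8.3.3.2 and Supplement 2.5.7 conflict on whether the missing-data sensitivity analysis will be done. As the Supplement reads, the choice follows sight of by-arm results, has no stated criterion, and relies partly on completion rates that do not register scores lost through stopping treatment.

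Second, Supplement 2.5.4 and 2.1.1 treat the same patients in opposite ways. Followed as written, the plan removes a patient with a baseline score who dies within the death-rule window before any post-baseline form. Deaths before Day 43 put the ceiling at about 13 control and 9 to 10 neratinib patients per 300, given exponential survival at the planning medians. The documents do not allow the actual number, or the arm it would favor, to be stated.

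Type I error for PFS and OS is not affected. The effect is on how far the quality-of-life results can be relied on. This should be corrected, but it does not threaten the primary conclusions.

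**What to change.** **Supplement 2.5.7.** Restore the SAP commitment. State that a pattern-mixture sensitivity analysis will be done, without condition, for the seven scales listed in section 2.5.3. Fix the patterns (for example by time of, or reason for, stopping treatment) and the identifying assumptions before any by-arm results are seen, and add the output to Table 2. Delta adjustment is one option. Modelling scores after death is not required, but the text should say how death is handled.

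**Supplement 2.5.4.** Define the time-to-deterioration population as all safety-population patients with a baseline score on that scale. Count deaths under the existing rule, and censor at baseline those with no post-baseline score and no qualifying death. The requirement for a post-baseline score can stay for the change-from-baseline analyses.

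**Cost.** Wording in two sections of the Supplement and a few extra tables. No new data are needed.
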